##### Exclusion Criteria

1. history of severe DN, active lower limb ulceration or lower limb amputation directly caused by diabetic neuropathy, or risk factors for any other causes of neuropathy (e.g. active hepatitis C, end stage renal disease, systemic lupus erythematosus or a known hereditary neuropathy) as determined through medical history, family history, history of medications, occupational history, history of exposure to toxins, physical and neurological examinations);

2. history of recent severe hypoglycemia (within prior 6 months) as defined by hypoglycemia resulting in coma or seizure or a history of recurrent diabetic ketoacidosis (DKA) or any diabetic ketoacidosis within the last three months.
3. history of persistent macroalbuminuria [random urine microalbumin creatinine ratio (ACR) >300 mg/gm]. ACR up to 300 mg/gm is acceptable if serum creatinine is <1.4 for women, <1.5 for men AND estimated GFR (eGFR) is > 60;
4. serum creatinine >1.4 for women and >1.5 for men or eGFR <60 [possible chronic kidney disease stage 3 or greater calculated using the Modification of Diet in Renal Disease (MDRD) equation];
5. pregnancy or lactation, or intention to become pregnant in next 12 months;
6. history of previous lung, kidney, pancreas, liver, cardiac or bone marrow transplant;
7. history of drug or alcohol abuse within the previous 5 years, or current weekly alcohol consumption >10 units/week;
8. use of warfarin (Coumadin), clopidogrel (Plavix), dipyridamole (Persantine), heparin or other anticoagulants, probenecid (Benemid, Probalan), sulfinpyrazone (Anturane) or other uricosuric agents; Subjects must agree to not use high-dose aspirin during the course of the study. Daily low-dose aspirin treatment (not more than 81 mg per day) may be continued if currently prescribed.
9. requiring long-term glucocorticoid therapy or chronic immunosuppressive therapy; Inhaled steroid use for management of asthma is not an absolute exclusion.
10. use of lithium
11. participation in an experimental medication trial within 3 months of starting the study;
12. current therapy for malignant disease other than basal- cell or squamous-cell skin cancer;
13. history of gastrointestinal bleeding or active gastric ulcer; screening laboratory abnormalities including AST (SGOT) and or ALT (SGPT) > 2.5 x the upper limit of normal (ULN), total bilirubin > 1.5 x ULN, platelets < 100,000;
14. developed keloid scarring in the past. Keloids are large, thick masses of scar tissue. These are more common among dark-skinned people.
15. presence of any condition that, in the opinion of the investigator would make it unlikely for the subject to complete 12 months of study participation, e.g., history of non-adherence to therapeutic regimens, presence of conditions likely to limit life expectancy, living situation that would interfere with study visit schedules such as a job requiring frequent or extended travel
16. known hypersensitivity to salsalate. Patients who have experienced asthma, hives, or other allergic-type reactions to aspirin or other NSAIDs are excluded from participation.

Patients with known or suspected aspirin or NSAID-sensitive asthma are excluded.

In addition, subjects with concurrent chicken pox, influenza, flu-like symptoms or other symptomatic viral illnesses should not be enrolled in the study until the illness or condition has resolved.

Subjects with known or suspected hypersensitivity to lidocaine or epinephrine may not be able to participate as these agents are used for local anesthesia during skin biopsies. The study investigators should consider the nature and severity of past reported reactions to these agents, and may consider alternative anesthesia options for local anesthesia on a case by case basis.

*\*Because obtaining the sural nerve response can be technically challenging, the absence of response does not necessarily indicate advanced neuropathy. Criteria for peroneal motor nerve conduction velocity is added as a secondary measure of neuropathy severity so that otherwise eligible candidates are not excluded based solely on inability to obtain the sural response.*

## 5. TRIAL TREATMENTS

### 5.1. Allocation to Treatment

Randomization to Salsalate or Placebo: After signing informed consent, confirming eligibility and completion of baseline assessments (visit 2), subjects will be randomized to salsalate, up to 3 grams/daily or matched placebo for 12 months. Randomization will be stratified by baseline HbA1c ( $\leq 8.0\%$  or  $> 8.0\%$ ).

Procedure for Subject Treatment Assignment: Subjects will be randomized to treatment with either Salsalate or Placebo. The procedures for randomization will be determined by the study biostatistician.

#### Breaking the Blind

In the event of an emergency and a need to know study medications, the investigator will contact Belmar Research Pharmacist (the research pharmacy contracted for this study) and request identification of subject's test article assignment. The Belmar Pharmacist will indicate that the blind was broken on the Pharmacy Randomization Log and will document the date of the request, the name of the research personnel making the request, and the pharmacist's signature. The research coordinator will report the emergent event on the Adverse Event CRF and the unmasking event on the Unmasking Report CRF and then signed by the investigator.

### 5.2. Study Drug

[figure not shown]
This study will be conducted under IND 113650 ([name], Sponsor-Investigator).

Neither subjects nor their insurance will incur any additional cost from their participation in this study. Salsalate and matching placebo will be provided by Belmar Research Pharmacy.

#### 5.2.1. Description of drug product

Salsalate tablets 500mg

Salsalate is a nonsteroidal anti-inflammatory agent for oral administration. Chemically, salsalate (salicylsalicylic acid or 2 hydroxy-benzoic acid, 2-carboxyphenyl ester) is a dimer of salicylic acid; its structural formula is shown below:

#### 5.2.2. Preparation and Dispensing

The Belmar Research Pharmacy will act as the central pharmacy for this study, and will provide salsalate and matching placebo to each participant.

#### 5.2.3. Administration

Each subject will be given sufficient study medication to last until the next scheduled visit.

Subjects will be instructed to take one tablet with breakfast for the first four days beginning with the first breakfast after receipt of the study medication. The study medication dose will be increased slowly to the maximum tolerated dose (2 tablets, 3 times daily) using the following schedule: Beginning on day 5, take 1 tablet with breakfast and 1 tablet with lunch. Beginning on day 9, take 1 tablet at breakfast, 1 tablet at lunch, 1 tablet at dinner. Beginning on day 23, take 2 tablets at breakfast, 1 tablet at lunch, 1 tablet at dinner. Beginning on day 27 take 2 tablets at breakfast, 2 tablets at lunch, 1 tablet at dinner. The maximum dose of study medication, 2 tablets at breakfast, 2 tablets at lunch, and 2 tablets at dinner, may be started no sooner than the 31st day from receiving the first supply of study medication. Should side effects (e.g., stomach upset, tinnitus) develop, the subject will be instructed to contact the study staff for guidance re: reducing the dose of study medication.

#### 5.2.4. Compliance

The number of tablets dispensed at each visit will be recorded in the case report form. Subjects are reminded to return all unused study medication at each visit in the original container. The study staff will collect all unused medications and record the number of tablets remaining. Discrepancies between expected versus actual study medication returned will be evaluated by the local study staff to address issues related to non-adherence to the study protocol. Subjects will be encouraged to continue on the maximally tolerated dose of study medication for the duration of the treatment period. Consistent with the intention to treat model, all subjects will be followed for the duration of the study treatment period according to the treatment schedule, unless consent is withdrawn, or, in the opinion of the investigator, it is unsafe for the subject to continue participation.

### **5.3. Drug Storage and Drug Accountability**

The Belmar Research Pharmacy shall be responsible for storage and dispensing of study drug for the cohort of subjects followed at the University of Michigan and Henry Ford Health System. The clinical coordinator will be responsible for drug accountability. Upon the completion of drug accountability, the coordinator will discard the remaining drug in a University of Michigan pharmaceutical bin.

### **5.4. Concomitant Medication(s)**

The research staff will record in the source documents all concomitant drugs used by the subject. This is to include prescription, non-prescription, homeopathic medications and dietary/vitamin supplements. At the screening visit, medication use is to be carefully reviewed to ensure that no contraindicated medications as described in the protocol are being used (e.g., blood thinning agents, immune-modulating medications, NSAIDS). At all subsequent visits, subjects will be asked to report any changes to their reported medication use and the source document updated accordingly. Queries regarding medication exclusions and contraindications are directed to the study co-chairs.

## **6. STUDY VISITS**

The schedule of study assessments is shown in Table 1. After obtaining informed consent, verifying eligibility at screening and completing all required baseline assessments, subjects are randomized, receive study medication and are followed every 3 months for one year. The staff should query the subject regarding any changes to their health, changes to their medication regimen, including changes in their insulin treatment, and frequency and severity of hypoglycemia.

Visits 4 and 6 may be conducted remotely if the study investigator agrees that a remote visit is appropriate for the participant, and the participant has access to a University of Michigan/Michigan Medicine affiliated laboratory. The remote visit option for Visits 4 and 6 will reduce the burden of study participation for those participants who live at a distance from the study site, or have limited ability to take time off from work or have other limiting obligations, or who are concerned about travel during the COVID-19 pandemic. Study staff will conduct the visit via telephone or site-approved and HIPPA compliant electronic conferencing platform. Study staff will place an order for required laboratory assessments and instruct the participant to have the laboratory measures obtained at the nearest Michigan Medicine affiliated laboratory.

### **6.1. Recruitment/Screening**

#### Visit 1: Screening/Eligibility

An eligibility visit will be scheduled for subjects who, based on preliminary screening (telephone, email, medical chart review) meet the general entry criteria (age, T1DM, diabetes duration, symptomatic peripheral neuropathy, no contraindications for salsalate, etc.). At visit 1 the investigator or her designee will obtain written informed consent, after which all required eligibility examinations will be performed. The eligibility examination will include the following laboratory assessments: HbA1c, metabolic comprehensive panel (METCOMP), complete blood count with platelets (CBCP), thyroid stimulating hormone (TSH), lipid profile, cystatin-C, uric acid, urine albumin assessment, and in all women of child bearing age and potential, a urine

pregnancy test, even if an accepted method of contraception is being used. If any of the required laboratory measures are documented in the subject's medical record as being completed in the prior 3 months (1 month for HbA1c, and 6 months for urine albumin), they will not need to be repeated at the screening visit. Additional blood and urine will be obtained for Luminex assays of inflammatory markers. The Luminex assays though may be postponed until the baseline examination.

Weight, height and seated blood pressure and pulse will be obtained.

A structured neurologic history and physical examination and nerve conduction studies will be performed at the screening visit to verify and document the presence of signs or symptoms of peripheral neuropathy, the presence of a sural nerve response, and abnormality of at least one abnormal nerve attribute (amplitude, latency, conduction velocity or f-wave) in the sural, peroneal or ulnar nerve. In the absence of a sural nerve response (e.g., sural amplitude is 0  $\mu$ V, response is unobtainable, then the presence of a peroneal motor nerve conduction velocity of  $\geq$  35 meters per second will be required for inclusion. Quantitative sensory testing will also be conducted at the screening visit.

All visit 1 measures are ideally to be completed within a 4-week time frame but may take up to 6 months (180 days) if repeated measures are needed, and may be done at one, or over several visits if that is more convenient for the subject.

## 6.2. Baseline

### Visit 2: Baseline (Day 0).

The key activities of the baseline visit are to obtain the initial skin biopsies and to initiate treatment with either Salsalate or placebo. Cardiovascular autonomic neuropathy (CAN) assessment, as well as quality of life and symptom questionnaires, and a short battery of functional assessments, will also be performed at the baseline visit. Two skin biopsies are obtained; one at the proximal thigh, and one at the distal leg. These will be done on the subjects' dominant side unless contraindicated (e.g., presence of a cast).

Upon satisfactory completion of all eligibility and baseline assessments, including the skin biopsy, a 3 month + 14-day supply of Salsalate or placebo will be provided, and written instructions for use of the medication reviewed with and provided to the subject. Subjects will be instructed to take one tablet with breakfast for the first four days beginning with the first breakfast after receipt of the study medication. The study medication dose will be increased slowly to the maximum tolerated dose (2 tablets, 3 times daily) using the following schedule: Beginning on day 5, take 1 tablet with breakfast and 1 tablet with lunch. Beginning on day 9, take 1 tablet at breakfast, 1 tablet at lunch, 1 tablet at dinner. Beginning on day 23, take 2 tablets at breakfast, 1 tablet at lunch, 1 tablet at dinner. Beginning on day 27 take 2 tablets at breakfast, 2 tablets at lunch, 1 tablet at dinner. The maximum dose of study medication, 2 tablets at breakfast, 2 tablets at lunch, and 2 tablets at dinner, may be started no sooner than the 31st day from receiving the first supply of study medication.

Subjects are to be reminded to return any unused study medication at their next visit.

Study staff will contact the subject within one week of the baseline visit to assess medication compliance and tolerance and to inquire as to the status of the biopsy sites.

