**Table 1: Proposed Visit Schedule for TINSAL-T1DN Study**

Visit Number	Visit 1	Visit 2	Visit 3	Visit 4**	Visit 5	Visit 6**	Visit 7
Visit Description	Screening	Baseline	Monitoring	Monitoring	Monitoring/ Outcomes	Monitoring	Monitoring/ Outcomes
Time point	Day -180 to 0	Day 0	Month 1	Month 3	Month 6	Month 9	Month 12
Visit window		NA	± 7 days	± 14 days	± 14 days	± 14 days	± 14 days
Informed Consent	X						
Medical History /Physical Examination†	X	X		X	X	X	X
Laboratory Measures*	X			X	X	X	X
Skin Biopsies (proximal/distal leg)		X					X
Neurological History /Physical Examination†	X						X
Nerve Conduction Studies	X						X
Neuropathy Total Symptom Score	X	X			X		X
Cardiovascular Autonomic Studies		X					X
Resting Heart Rate		X	X	X	X	X	X
Quantitative Sensory Testing	X						X
NeuroQOL		X			X		X
Survey of Autonomic Symptoms		X			X		X
Neuropathy Pain Scale		X			X		X
Functional Assessments							
Berg Balance Scale							
8-foot Get Up and Go Test		X					
Modified Falls Efficacy Scale							X
Medication Dispensing§		X		X	X	X	
Medication Compliance			X	X	X	X	X
Medication Return				X	X	X	X
Adverse Events Monitoring		X	X	X	X	X	X

† Baseline history and examination will include diabetes duration, diabetes complications, diabetes treatment, concurrent medical problems, relevant past surgical history, height, weight, blood pressure and pulse, and foot examination. Follow up visits will include changes in medical or surgical history, weight, blood pressure, pulse and foot examination \* HbA1c, Metabolic Comprehensive Panel, Complete Blood Count with Platelets, TSH, Lipid Profile, Cystatin-C, Uric Acid and Urine Albumin performed at screening visit (unless results for these tests are documented in the medical record as being done in the prior 3 months for all except HbA1c (1 month) and Urine Albumin (6 months). Urine pregnancy test at screening for all women of childbearing potential regardless of contraceptive practiced. HbA1c, Metabolic Comprehensive Panel, CBCP, Cystatin-C, Uric Acid and Urine Albumin will be repeated at 3, 6, 9 and 12 months of follow-up. Lipids will be repeated at 3, 6 and 12 months of follow-up. Luminex inflammatory marker assays on blood and urine performed at screening or baseline, and again at study end.

\*Visit windows for visit 3-7 are based off when the patient starts the study medication following visit 2 due to the shipping of the medication from Belmar Pharmacy directly to the participant.

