#### Visit 7: Final Visit (Month 12).

Weight, blood pressure and resting heart rate are recorded and inquiries made re: changes in health status or physical symptoms. Laboratory assessments (HbA1c, METCOMP, CBCP, cystatin-C, lipids, uric acid and urine albumin) will be obtained as will blood and urine samples

for Luminex assays of inflammatory markers. Urine pregnancy testing may be performed at the discretion of the investigator for all women of childbearing potential. The study staff will collect any unused study medication. The number of unused salsalate tablets will be recorded in the source document and unused medication secured until returned for final drug disposition.

The structured neurological history and examination and nerve conduction studies performed at screening will be repeated.

Cardiovascular autonomic neuropathy (CAN) assessment, quantitative sensory tests, as well as quality of life and symptom questionnaires, and battery of functional assessments, will be performed at the final visit. Two skin biopsies are obtained; one at the proximal thigh, and one at the distal leg. These will be done on the subjects' dominant side unless contraindicated (e.g., presence of a cast). The biopsies will be obtained from skin which is adjacent (within 1 cm) to the original biopsy sites.

Within 1 week of the final visit, the study staff will contact the subject by phone or email to inquire about any changes in health status, and to inquire as to the status of the skin biopsy sites.

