#### **6.4. Scheduled Interim Contact**

Within 1 week of Visit 2 (Baseline, initial biopsy) the study staff will contact (telephone, email, in-person) the subject to inquire about any problems at the biopsy sites and to inquire about medication compliance and any side effects encountered. This contact will be recorded in the source document.

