### 9. EXPECTED RISKS ASSOCIATED WITH THE PROTOCOL

#### 9.1. Risks Associated with Study Participation

Risks associated with study participation in general are related to the time commitment for the study, and risk for loss of privacy. There will be 7 "in-person" visits required for the study, as well as 2-3 "remote" visits conducted by phone or email. The study staff will try to minimize the burden of the visits to the extent practical by scheduling on days and at times that are most convenient for the patient. Privacy risks will be reduced by maintaining a separate research record that uses a coded identifier, rather than personal identities. Links to the coded identifier and personal identity shall be maintained in a secure electronic file by the study coordinator and the links will ultimately be destroyed. Destruction of the links will occur no sooner than 2 years after the study has been acknowledged as terminated by the University of Michigan IRB (UM IRBMED).

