#### **9.5. Risks Associated with Skin Biopsies**

The risks associated with skin biopsies are pain, bleeding, bruising, or infection. Subjects may be left with a small scar or discolored area at each biopsy site. Four sites are biopsied in the course of the study, each about 3 mm in diameter. The skin biopsies will be done by members of the staff who have training and experience in doing them. The areas biopsied will be cleaned with antiseptics prior to the biopsy and a local anesthetic used to reduce pain. Subjects will be given written information about wound care and how and when to report any signs or symptoms of infection. The study staff will call the subject within one week each biopsy to check on how it is healing.

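### The one-week compliance and tolerance contact is counted from Visit 2, but drug is shipped afterwards and Visits 3-7 are counted from medication start, so the contact can precede the first dose

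*Combined protocol and SAP*

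**What the plan says.** Section 6.2 (Visit 2) sets the contact: "Study staff will contact the subject within one week of the baseline visit to assess medication compliance and tolerance". Section 6.4 describes the same contact, also within one week of Visit 2, and gives it two purposes: "to inquire about any problems at the biopsy sites and to inquire about medication compliance and any side effects encountered". Neither section sets an earliest day, requires that dosing has begun, or asks for a repeat call if it has not.

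Four other places bear on the timing:

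- **Table 1 footnote:** "Visit windows for visit 3-7 are based off when the patient starts the study medication following visit 2". The reason given is that the pharmacy ships drug straight to the participant.
- **Section 5.1:** randomization follows completion of the Visit 2 assessments, so assigned drug cannot be shipped earlier.
- **Section 5.2.3** (repeated in 6.2): one tablet a day "beginning with the first breakfast after receipt of the study medication", followed by a stepwise increase.
- **Section 9.5**, on the biopsies: "The study staff will call the subject within one week each biopsy to check on how it is healing".

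The next point at which staff are told to assess compliance and tolerance is Visit 3 (Month 1, ± 7 days), in section 6.3.

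**The concern.** The contact does two jobs that run on different clocks. The biopsy-site question belongs to Visit 2, because the biopsies are taken there. The compliance and tolerance question belongs to the first dose. The protocol treats the gap between the two dates as large enough to re-anchor five visits, yet leaves on the old anchor the one contact for which a few days matter most. The Summary of Changes records the re-anchoring of Table 1 in September 2022 and lists no matching change to 6.2 or 6.4, so an incomplete update is the likely explanation.

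Before Visit 3 this is the only scheduled occasion on which staff ask about tolerance. Participants use insulin, and section 9.3 warns of hypoglycemia, gastrointestinal effects and tinnitus, to be managed by adjusting insulin or reducing the study dose. If the contact comes before dosing, the first three to five weeks of titration are covered only by what participants report on their own initiative. Tolerability has already mattered in this trial: section 3 says the 2017 design change was made partly because discontinuation of study medication differed between groups. The documents do not say how early those discontinuations occurred.

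**Working it through.** The plan gives no figure to reproduce. The check is a timeline.

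**Inputs**

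- Visit 2 is day 0; the contact falls on day *d*, at most day 7 (6.2, 6.4).
- *L* is the number of days from Visit 2 to the first dose. Shipping time is not stated, so *L* is an assumption and is varied. If drug arrives after breakfast, *L* is the day of receipt plus 1.
- Product: "Salsalate tablets 500mg" (5.2.1).
- Visit 3 falls at Month 1 ± 7 days from medication start (Table 1).

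**Scheduled dose by dosing day (5.2.3)**

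| Dosing day | Tablets/day | Dose (tablets × 0.5 g) |
|---|---|---|
| 1-4 | 1 | 0.5 g |
| 5-8 | 2 | 1.0 g |
| 9-22 | 3 | 1.5 g |
| 23-26 | 4 | 2.0 g |
| 27-30 | 5 | 2.5 g |
| 31 onward | up to 6 | up to 3.0 g |

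**Step 1: what the contact sees.** A contact on day *d* falls on dosing day *d* − *L* + 1. There is no exposure if *L* > *d*.

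| Contact day *d* | Lag *L* (days) | Dosing day at contact | Scheduled dose seen |
|---|---|---|---|
| 7 | 0-3 | 8 to 5 | 1.0 g/day |
| 7 | 4-7 | 4 to 1 | 0.5 g/day |
| 7 | 8 or more | none | none |
| 5 | 0-1 | 6 to 5 | 1.0 g/day |
| 5 | 2-5 | 4 to 1 | 0.5 g/day |
| 5 | 6 or more | none | none |
| 3 | 0-3 | 4 to 1 | 0.5 g/day |
| 3 | 4 or more | none | none |

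If drug arrives after breakfast on day 7 or later, then *L* is at least 8 and every permitted contact day precedes the first dose.

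**Step 2: the next scheduled check.** With Month 1 taken as day 30, Visit 3 falls on dosing days 30 − 7 = 23 to 30 + 7 = 37. The schedule is then at 4 tablets (2.0 g/day) when the window opens and up to 6 tablets (3.0 g/day) from day 31. If Month 1 is read as 28 days, the window opens on day 28 − 7 = 21, at 3 tablets (1.5 g/day).

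**Step 3: the contact counted from first dose.** On dosing days 5-7 the schedule is at 2 tablets (1.0 g/day) whatever the lag. Dosing day 5 is day *L* + 4 after Visit 2, which is within the biopsy week when *L* + 4 ≤ 7, that is, *L* ≤ 3.

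**The case against.** The strongest objection is that the documents show a possibility and not a frequency. Shipping time is unstated, and a day-7 contact sees some exposure at every lag up to 7 days. The one-week limit is an outer bound, so staff are free to wait until day 7. Section 6.2 also still lists starting treatment among the key activities of Visit 2 and says the supply is provided once baseline assessments are complete, and Table 1 marks dispensing at that visit. That suggests a short intended lag. This stands as a limit on how often the problem arises. It does not remove the problem: the footnote states outright that drug is shipped after the visit, and nothing in 6.2 or 6.4 tells staff to wait or to call again.

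A second objection is that little is lost. The dose in the first week is 0.5-1.0 g/day, section 9.3 links hypoglycemia especially to high doses, and it says gastrointestinal and ear effects usually subside. Participants are told to contact staff about side effects and to check glucose often. The compliance question would itself show that drug had not been started. All of this is fair, and it keeps the point modest.

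A third objection is that the repair buys little. After a contact on dosing days 5-7, the rise to 1.5 g/day on day 9 and beyond still has no staff-initiated check until Visit 3, a gap of about 16 days (23 − 7) to 32 days (37 − 5). That is true, but the protocol chose to have one early check, and the change only ensures that this check covers some exposure.

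**Conclusion.** The concern holds. A contact that complies fully with 6.2 and 6.4 can fall before the first dose. The next scheduled tolerance check is then Visit 3, at about dosing day 23-37 and at least 2.0 g/day (day 21 and 1.5 g/day if a month is read as 28 days). The ordering rests on current text alone. How often it happens depends on the shipping time and on the day staff choose to call, and the documents give neither. For a day-7 contact the check is lost altogether only with a lag of 8 days or more; earlier contacts lose it sooner.

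This is an operational early-safety gap of modest severity. It has no bearing on type I error, power or the primary analysis. It merits correction because the rule has the wrong anchor and the remedy is cheap.

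**What to change.** In 6.2 and 6.4, split the contact by purpose:

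- Keep the biopsy-site contact within one week of Visit 2, as 9.5 requires.
- Make the compliance and tolerance contact within one week after the first dose, for example on dosing days 5-7, using the medication-start date that the Table 1 windows already need.
- Where drug starts within 3 days of Visit 2, allow one contact to serve both purposes.

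Visit 3 and the titration stay as they are.

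The cost is protocol wording and at most one extra call or email per participant, so at most 70 in total, and none where the lag is 0-3 days. The burden is already described to participants: section 9.1 speaks of 7 in-person "visits required for the study, as well as 2-3" remote ones by phone or email. The text schedules only two of these, the one after Visit 2 and the one after Visit 7 ("Within 1 week of the final visit, the study staff will contact the subject by phone or email"), so a third fits.
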